## 9.3 VARIABLES

### 9.3.1 Exposures

The study is descriptive in nature. It will not assess the association between any exposure and outcomes.

### 9.3.2 Outcomes

#### 9.3.2.1 Primary outcomes

For all the three waves of CNSR, the following primary outcomes will be assessed:

- Proportion of patients who received IV-rtPA treatment within 3h of symptom onset (patient group C, please refer to [Figure 1](#) for details on patient groups) among 2h IVT-eligible patients (patient group B);
- Proportion of patients who received IV-rtPA treatment within 4.5h of symptom onset (patient group C') among 3.5h IVT-eligible patients (patient group B').

#### 9.3.2.2 Secondary outcomes: the analysis will be performed for each wave of CNSR

Among all AIS patients (patient group A), the following secondary outcomes will be assessed:

[figure not shown]
- Proportion of patients who arrived at hospital within 2h of symptom onset and who received IV-rtPA treatment within 3h of symptom onset (patient group C);
- Proportion of patients who arrived at hospital within 3.5h of symptom onset and who received IV-rtPA treatment within 4.5h of symptom onset (patient group C');

Among 3h IV-rtPA-treated patients (patient group C), the following secondary outcomes will be assessed

- The door-to-needle (DTN) time (time between arrival at hospital and the administration of IV-rtPA treatment);
- Proportion of patients DTN time  $\leq$  60 minutes (min);
- Time between symptom onset and arrival at hospital;
- Time between symptom onset and the administration of IV-rtPA treatment.

Among 4.5h IV-rtPA-treated patients (patient group C'), the following secondary outcomes will be assessed

- The DTN time;
- Proportion of patients DTN time  $\leq$  60 min;
- Time between symptom onset and arrival at hospital;
- Time between symptom onset and the administration of IV-rtPA treatment.

## 9.4 DATA SOURCES

The current study will be conducted based on data collected from the three waves of CNSR.

CNSR I (2007-2008) used IS patient data from 132 hospitals in China, including 100 tertiary and 32 urban hospitals. Ischemic stroke patients aged 18 years and older within 14 days of symptom onset were included for the study. Paper-based registry forms (PRF) developed by the expert advisory panel were used for data collection. Patient information including demographics (age, gender, etc.), NIHSS, medical history (diabetes mellitus, hypertension, coronary heart disease/previous myocardial infarction, atrial fibrillation, previous stroke, TIA, dyslipidemia), symptom onset-to-door time, health insurance schemes (urban basic medical insurance schemes for urban and governmental employees and urban residents, new rural cooperative medical schemes for rural residents, commercial insurance, and self-payment [\[P20-03289\]](#)), vascular risk factors, imaging [mainly magnetic resonance imaging (MRI) or magnetic resonance angiography (MRA)], blood sampling, time-related variables [symptom onset time, hospital arrival time, CT time, IV-rtPA treatment time, etc.], implementation of performance measures for acute stroke care, final diagnosis, length of stay, in-hospital death, and follow-up information for 3-month, 6-month, and 12-month was collected. Hospital-level information including geographic region (e.g., east, central, or west, according to the annual report on health statistics of China [\[R20-1011\]](#)), teaching status, hospital bed size, and annual stroke volume was collected [0](#).

CNSR II (2012-2013) used IS patient data from 219 hospitals in China. IS patients aged 18 years and older within 7 days of symptom onset were included for the study. Web-based case report forms (CRF) were used for data collection. Patient information including

demographics, NIHSS, medical history, symptom onset-to-door time, health insurance schemes, vascular risk factors, imaging, blood sampling, time-related variables, implementation of performance measures for acute stroke care, final diagnosis, length of stay, modified Rankin scale at discharge, and in-hospital death was collected. Follow-up information for 3-month, 6-month, and 12-month was collected by phone interview. Hospital-level information including geographic region, teaching status, hospital bed size, and annual stroke volume was collected [\[P20-03289\]](#).

CNSR III (2015-2017) used AIS or TIA patient data from 201 hospitals in China. AIS or TIA patients aged 18 years and older within 7 days of symptom onset were included for the study. An electronic data collection (EDC) system was used through an electronic software or the internet. Patient information including demographics, NIHSS, medical history, symptom onset-to-door time, health insurance schemes, vascular risk factors, imaging, blood sampling, time-related variables, implementation of performance measures for acute stroke care, final diagnosis, length of stay, modified Rankin scale at discharge, and in-hospital death was collected. Follow-up information for 3-month, 6-month, and 12-month was collected by phone interview. Hospital-level information including geographic region, teaching status, hospital bed size, and annual stroke volume was collected.

## 9.5 STUDY SIZE

It was estimated that in CNSR I, II, and III, the number of total AIS patients is 14704, 19604, and 15204, respectively.

Assuming the IV-rtPA-treated among IVT-eligible patients in CNSR I, II, and III are 4%, 5%, and 28% with the 95% confidence interval (CI) for each wave as below, then which can be distinguished with current study size.

CNSR	I	II	III
Assumed IV-rtPA proportion among eligible patients % (95% CI)	4% (3.7-4.3%)	5% (4.7-5.3%)	28% (27.3-28.7%)

No formal sample size calculation is performed due to the nature of this study. All eligible AIS patients within the existing database from the three waves of CNSR will be included in this study.

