

● Proportion of patients DTN time <math>\leq</math> 60 minutes (min);

● Time between symptom onset and arrival at hospital;

● Time between symptom onset and the administration of IV-rtPA treatment.

 
Among 4.5h IV-rtPA-treated patients (patient group C'), the following secondary outcomes will be assessed:
 

● The DTN time;

● Proportion of patients DTN time <math>\leq</math> 60 min;

● Time between symptom onset and arrival at hospital;

● Time between symptom onset and the administration of IV-rtPA treatment.

		
    		

Name of company: Boehringer Ingelheim			
Name of finished medicinal product: Actilyse			
Name of active ingredient: Alteplase			
Protocol date: 17 Apr 2020	Study number: 0135-0343	Version/Revision: 1.1	Version/Revision date: 12 Mar 2020
[REDACTED]			

Name of company: Boehringer Ingelheim										
Name of finished medicinal product: Actilyse										
Name of active ingredient: Alteplase										
Protocol date: 17 Apr 2020	Study number: 0135-0343	Version/Revision: 1.1								
Data sources:	CNSR I, II, and III									
Study size:	
It was estimated that in CNSR I, II, and III, the number of total AIS patients is 14704, 19604, and 15204, respectively.
 
Assuming the IV-rtPA-treated among IVT-eligible patients in CNSR I, II, and III are 4%, 5%, and 28% with the 95% confidence interval (CI) for each wave as below, then which can be distinguished with current study size.
 
  
 CNSR	Wave I	Wave II	Wave III	
   
 Assumed IV-rtPA proportion among eligible patients % (95% CI)	4% (3.7-4.3%)	5% (4.7-5.3%)	28% (27.3-28.7%)	
  
		CNSR	Wave I	Wave II	Wave III	Assumed IV-rtPA proportion among eligible patients % (95% CI)	4% (3.7-4.3%)	5% (4.7-5.3%)	28% (27.3-28.7%)
CNSR	Wave I	Wave II	Wave III							
Assumed IV-rtPA proportion among eligible patients % (95% CI)	4% (3.7-4.3%)	5% (4.7-5.3%)	28% (27.3-28.7%)							

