Till 2017, three waves of CNSR were completed: 2007-2008 (CNSR I), 2012-2013 (CNSR II), and 2015-2017 (CNSR III). The number of hospitals participating each of CNSR were 132, 219, and 201, respectively. When compared to CNSR I, data from CNSR II showed a 1.17-fold increase in the adjusted odds of delivering evidence-based performance metrics for ischemic stroke (IS) care. Nevertheless, no statistically significant difference in the proportion of patient who received intravenous thrombolytics (IVT) treatment within 3 hours (h) of symptom onset was observed between the two CNSR [P20-03289].

In China, IV-rtPA was approved for the treatment of AIS patients within 3h of symptom onset without absolute contraindications. However, in 2008, the European Cooperative Acute Stroke Study (ECASS) III study concluded that AIS patients could still benefit from IV-rtPA treatment when given between 3h and 4.5h [P08-12177]. The Chinese treatment guideline for AIS was updated in 2010, for which a recommendation of IV-rtPA treatment within 3h to 4.5h of symptom onset was added [P20-03291].

The current study aims at evaluating differences, if any, in clinical practice of IV-rtPA treatment among AIS patients from 2007 to 2017. In addition, the study will also provide information on the demographic and clinical characteristics of AIS patients receiving IV-rtPA in China. Taken together, the study will help us to better understand the trend of clinical practices for AIS treatment in China during the last decade, especially after the update of the

national AIS treatment guideline and the continuous efforts made by academic society and MOH in the field of stroke care.

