**2) IVT-eligible patients (patient groups B and B')**

1. Inclusion criteria:

- (1) Met the in- and exclusion criteria of "all AIS patients"
- (2) Arrived at hospital within 2h (patient group B) or 3.5h (patient group B') of symptom onset

2. Exclusion criteria:

- (1) Missing key data including
  - i. symptom onset time (or last known well time);
  - ii. hospital arrival time;
  - iii. whether received IVT treatment or not;
  - iv. the time of IVT treatment
- (2) Documented IVT absolute contraindications, according to the case report form (CRF) for each wave of CNSR (please refer to [ANNEX 3](#) for details)

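### The confidence intervals in Protocol 9.5 and the abstract are labelled for eligible patients but match the total AIS counts, so precision for the primary outcomes is overstated and separating wave I from wave II is unsupported

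*Protocol*

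**What the plan says.** Protocol section 9.5 gives one set of patient numbers: "the number of total AIS patients is 14704, 19604, and 15204, respectively". It then states the assumed treatment proportions, explicitly for eligible patients: "Assuming the IV-rtPA-treated among IVT-eligible patients in CNSR I, II, and III are 4%, 5%, and 28% with the 95% confidence interval (CI". The 95% intervals attached to them are 3.7-4.3%, 4.7-5.3% and 27.3-28.7%. The conclusion drawn is "then which can be distinguished with current study size", with no pair of waves named. The abstract repeats the table under the row label "Assumed IV-rtPA proportion among eligible patients % (95% CI". Section 9.5 also says: "No formal sample size calculation is performed due to the nature of this study".

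Both primary outcomes (Protocol 9.3.2.1, SAP 8.2.1) are proportions of group B or B'. Under Protocol 9.2 these groups must meet the criterion "Arrived at hospital within 2h (patient group B) or 3.5h (patient group B') of symptom onset". They also exclude patients with missing key times or a documented absolute contraindication. Group A, by contrast, allows arrival up to 7 days after onset. The SAP (Study Population, under 7.2) states that B and B' are subsets of A. The proportion treated among all AIS patients is a separate, secondary outcome in Protocol 9.3.2.2: "Among all AIS patients (patient group A), the following secondary outcomes will be assessed".

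**The concern.** The row is labelled for eligible patients, but the only counts beside it are for all AIS patients. If the intervals were computed on those totals, they describe the precision of a different quantity and are too narrow for the primary outcomes.

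This is the only precision statement for the primary outcomes in the readable text. The printed wave I and wave II intervals do not overlap (4.3% against 4.7%), so a reader will take a one-point change between those waves as resolved. Whether it is resolved depends on eligible counts that are not shown. As context only, Protocol section 7 reports an earlier comparison of waves I and II that found "no statistically significant difference in the proportion of patient who received intravenous thrombolytics (IVT) treatment within 3 hours (h) of symptom onset". The denominator of that comparison is not stated there, so it settles nothing, but section 9.5 does not address it.

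**Working it through.** **Inputs.** Total AIS counts of 14,704, 19,604 and 15,204, assumed proportions of 4%, 5% and 28%, and the printed intervals, all from Protocol 9.5. The eligible share f of all AIS patients is not in the readable text. It is treated below as an assumption, equal in each wave.

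**Step 1: reproduce the printed intervals.** Wald interval p ± 1.96·√(p(1−p)/n), with n the total AIS count:

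- Wave I: 0.04 ± 1.96·√(0.0384/14704) = 3.68-4.32%, printed 3.7-4.3%
- Wave II: 0.05 ± 1.96·√(0.0475/19604) = 4.69-5.31% (4.695-5.305%), printed 4.7-5.3%
- Wave III: 0.28 ± 1.96·√(0.2016/15204) = 27.29-28.71%, printed 27.3-28.7%

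All six limits round to the printed values. Wilson and Clopper-Pearson intervals round to the same values.

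**Step 2: find the smallest eligible count that could give the printed intervals.** Allowing for rounding, the half-width can be at most 0.35, 0.35 and 0.75 percentage points. Then n = 1.96²·p(1−p)/h²:

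- Wave I: 3.8416·0.0384/0.0035² ≈ 12,042, or 81.9% of 14,704
- Wave II: 3.8416·0.0475/0.0035² ≈ 14,896, or 76.0% of 19,604
- Wave III: 3.8416·0.2016/0.0075² ≈ 13,768, or 90.6% of 15,204

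**Step 3: widths on an eligible denominator.** With n = f × total, the width grows by 1/√f. The shares below are illustrations, not estimates.

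| f | n (I / II / III) | Wave I | Wave II | Wave III | Width factor | I and II intervals |
|---|---|---|---|---|---|---|
| 50% | 7,352 / 9,802 / 7,602 | 3.55-4.45% | 4.57-5.43% | 26.99-29.01% | 1.41 | separate |
| 20% | 2,941 / 3,921 / 3,041 | 3.29-4.71% | 4.32-5.68% | 26.40-29.60% | 2.24 | overlap |
| 10% | 1,470 / 1,960 / 1,520 | 3.00-5.00% | 4.04-5.96% | 25.74-30.26% | 3.16 | overlap |

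**Step 4: thresholds for wave I against wave II.**

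- Per-wave intervals just touch when f = [1.96·(√(0.0384/14704) + √(0.0475/19604))/0.01]² = 0.387. That is 5,686 and 7,581 eligible patients.
- The interval for the difference just reaches zero when f = [1.96·√(0.0384/14704 + 0.0475/19604)/0.01]² = 0.193. That is 2,844 and 3,792 eligible patients.

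**Step 5: wave III.** Even at f = 1% the intervals are 20.86-35.14% for wave III and 1.95-8.05% for wave II, so they remain separate.

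**Step 6: the SAP's wave I count.** The SAP gives 12,415 for wave I. The interval is then 3.66-4.34%, which rounds to the same printed values. The two thresholds in step 4 become about 42% and 21%.

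**The case against.** The strongest reply is that little depends on these intervals. The study is described as descriptive, it disclaims a formal sample size calculation, and it takes every eligible patient in an existing database. The SAP does not repeat the precision statement. Its mock Table 1 reports n/N with a 95% interval on the eligible denominators, so the results will carry their own correct precision. This stands and limits the consequence. It does not correct section 9.5 or the abstract, where the protocol chose to print intervals and draw a conclusion from them.

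The remaining objections qualify the numbers but leave the mismatch in place:

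- **Unseen text.** The patient-flow figure is not shown and some text is redacted, so eligible counts may exist there. The printed intervals would still match the totals.
- **Overlap is not a test.** At f = 20% the wave I and II intervals overlap, yet the interval for the difference is 0.02 to 1.98 points. The 39% threshold follows the protocol's own per-wave presentation. The 19% threshold is the one to use for the difference.
- **Equal f is a simplification.** The contraindication lists differ between CNSR I and the later waves, so the shares probably differ too.
- **Independence is assumed.** Clustering by hospital would widen the intervals further. The documents give no intraclass correlation, so this is not quantified.
- **No pair of waves is named.** The jump from 4-5% to 28% dominates the assumed figures and is not in doubt. But an unrestricted claim printed beside three non-overlapping intervals does cover wave I against wave II.

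**Conclusion.** The point holds: the printed intervals are wrong for the denominator on their label. They reproduce on the total AIS counts, whereas the label and both primary outcomes refer to restricted subsets. Precision is overstated by 1/√f, and f cannot be recovered from the readable text.

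The statement that the waves can be told apart is sound for wave III against waves I and II. For wave I against wave II it is unsupported rather than shown to be false. It would be true by the per-wave intervals if more than about 39% of AIS patients were eligible, and by the difference interval if more than about 19% were. Both figures assume equal shares across waves, independent patients and the protocol's wave I count. This should be fixed, but it affects a planning statement and not the estimates the study will report.

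**What to change.** 1. Obtain the group B and group B' counts for each wave with a count query on the existing data.
2. Recompute the intervals in Protocol 9.5 and the abstract on those counts, separately for the 2h/3h and 3.5h/4.5h outcomes. The protocol does not say which outcome the 4%, 5% and 28% belong to. State this, and give assumed proportions for the other outcome.
3. Restrict the conclusion to the contrasts those intervals support, naming the waves. An interval for the wave I to II difference is optional.
4. If counts cannot be obtained, delete the printed intervals and the wave I against II claim, or show intervals over stated assumed eligible denominators.

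Relabelling the row as all AIS patients is not a remedy. The assumed proportions are explicitly for eligible patients, and the all-AIS proportion is a different outcome. The wave I total (14,704 in the protocol, 12,415 in the SAP) should be reconciled separately.

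The cost is one query and a text correction in two places. The stated precision becomes less favourable. Populations, analyses and included patients do not change.

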## **8. RESEARCH QUESTION AND OBJECTIVES**

The present study is to be conducted based on the AIS patient data collected from CNSR I, II, and III.

The primary objectives are:

- To investigate the temporal changes in the proportion of IV-rtPA treatment from 2007 to 2017 among IVT-eligible patients (patient groups B and B') and overall AIS patients (patient group A) in China;
- To investigate the temporal changes in IV-rtPA treatment time intervals from 2007 to 2017 among IV-rtPA-treated patients (patient groups C and C') in China.

The secondary objectives are:

- To describe the demographic and clinical characteristics of the IV-rtPA-treated patients (patient groups C and C'), IVT-eligible patients (patient groups B and B') and the overall AIS patients (patient group A) from 2007 to 2017 from the CNSR I to III.

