7.2 SETTING

This study will use AIS patient data from CNSR I to III, stretching across a 10-year time frame from 2007 to 2017. CNSR is a nationwide, prospective stroke registry where patients with acute cerebrovascular diseases were continuously enrolled for 8-12 month every 5-year since 2007.

[REDACTED]

[REDACTED]

CNSR I (2007-2008) was conducted in 131 sites across China, including 113 tertiary and 18 urban hospitals, all the included ischemic stroke (IS) patients were older than 18 and within 14 days of onset. CNSR II (2012-2013) was conducted in 219 hospitals nationwide, and all the included IS patients were older than 18 and within 7 days of onset. CNSR III (2015-2017) was conducted in 201 hospitals, AIS or TIA patients aged 18 years and older within 7 days of symptom onset were included.

STUDY POPULATION

All eligible patients from the CNSR I to III will be included. It was estimated that in CNSR I, II, and III, the number of total AIS patient is 12415, 19604, and 15204, respectively.

The study will analyze data for the following patient groups:

(1) All AIS patients (patient group A): the overall AIS patients aged 18-80 years who arrived at hospital within 7 days of symptom onset;

(2) IVT-eligible patients (patient groups B and B'):

Patient group B and B' are subsets of patient group A: AIS patients who arrived at hospital within 2h (patient group B) and 3.5h (patient group B') of symptom onset and with no documented absolute contraindications to IVT treatment;

(3) IV-rtPA-treated patients (patient groups C and C'):

Patient group C is a subgroup of patient group B, while patient group C' is a subset of patient group B': IVT-eligible patients who arrived at hospital within 2h of symptom onset and received IV-rtPA within 3h of symptom onset (patient group C) and those who arrived at hospital within 3.5h of symptom onset and received IV-rtPA within 4.5h of symptom onset (patient group C').

The flow of data selection for each of the three reporting patient groups is depicted in Figure 1 below.

[figure not shown]

Figure 1. Patient groups selected for the time-trend study

The in- and exclusion criteria for each of the reporting groups are listed below:

All AIS patients (patient group A)

Inclusion criteria:

1. Aged 18-80 years
2. Diagnosed with AIS on admission

Exclusion criteria:

1. Missing baseline data including age and gender

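### The study-size confidence intervals use all AIS patients as N and ignore hospital clustering, so the claim that waves I and II can be distinguished is not supported

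*Protocol*

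**What the plan says.** Protocol 9.5 gives the total number of AIS patients per wave as 14704, 19604 and 15204. It then sets the assumed proportions, in the same words as the abstract: "Assuming the IV-rtPA-treated among IVT-eligible patients in CNSR I, II, and III are 4%, 5%, and 28" per cent. It attaches intervals of 3.7-4.3%, 4.7-5.3% and 27.3-28.7%, and continues "with the 95% confidence interval (CI) for each wave as below, then which can be distinguished with current study size". It adds that no formal sample size calculation is made and that all eligible patients in the database are used.

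The first primary outcome in protocol 9.3.2.1 is a proportion "among 2h IVT-eligible patients (patient group B"); the second uses B', the 3.5h group. SAP 7.2 says that B and B' "are subsets of patient group A: AIS patients who arrived at hospital within 2h (patient group B") or within 3.5h (B'), without a documented absolute contraindication. Group A takes arrivals up to 7 days. The SAP's own totals differ for wave I: "It was estimated that in CNSR I, II, and III, the number of total AIS patient is 12415, 19604, and 15204, respectively".

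On hospitals, protocol 7 states: "The number of hospitals participating each of CNSR were 132, 219, and 201, respectively". Protocol 9.6 says that they were chosen by convenience. The readable analysis text (protocol 9.7.1, SAP 11, and SAP Annex 1 Tables 1, 3.1, 3.2.1 and 3.2.2) asks for a 95% CI on proportions without naming a method.

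**The concern.** The row in 9.5 is labelled as a proportion among eligible patients, but the only counts given are for all AIS patients. If those counts were used as N, the intervals describe a much larger group than the one the outcome is measured in. They also assume independent patients. Treatment with IV-rtPA probably varies between hospitals, and the objective is worded for patients "and overall AIS patients (patient group A) in China", which reaches beyond the participating sites.

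Temporal change is the primary objective, and the readable tables carry it only through per-wave proportions with intervals. The assumed step from wave I to II is 1 percentage point, so the claim that these waves can be separated depends on the width of the intervals. Protocol 7 itself reports, from a cited study: "Nevertheless, no statistically significant difference in the proportion of patient who received intravenous thrombolytics (IVT) treatment within 3 hours (h) of symptom onset" between waves I and II. That outcome is related, but its denominator is not stated, so this is context and not proof.

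**Working it through.** **Inputs.** Totals of 14704, 19604 and 15204 and proportions of 4%, 5% and 28% (protocol 9.5); 132, 219 and 201 hospitals (protocol 7); the SAP's wave I figures of 12415 patients and 131 sites (SAP 7.2). Two inputs are assumptions because the documents do not give them: the eligible share f, taken as equal across waves, and the ICC.

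**Step 1: reproduce the plan's intervals.** Half-width = 1.96 × √(p(1−p)/N), with N = all AIS patients.

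- Wave I: 1.96 × √(0.04 × 0.96/14704) = 0.32 points, giving 3.68-4.32%.
- Wave II: 1.96 × √(0.05 × 0.95/19604) = 0.31 points, giving 4.69-5.31%.
- Wave III: 1.96 × √(0.28 × 0.72/15204) = 0.71 points, giving 27.29-28.71%.

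All three round to the printed values. Working backwards, the smallest N that rounds to each printed interval is 12042, 14896 and 13768, that is 82%, 76% and 91% of the totals. Shares that high are not plausible for a 2h or 3.5h arrival subset of a 7-day population. The SAP's wave I total gives 3.66-4.34%, which also rounds to 3.7-4.3%, so the difference between the two documents does not explain the problem.

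**Step 2: correct the denominator only.** Put N = f × total, with no clustering.

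| f | Wave I CI (%) | Wave II CI (%) | CIs overlap? | II−I difference, z |
|---|---|---|---|---|
| 100% | 3.68-4.32 | 4.69-5.31 | no | 4.46 |
| 50% | 3.55-4.45 | 4.57-5.43 | no | 3.15 |
| 30% | 3.42-4.58 | 4.44-5.56 | yes | 2.44 |
| 20% | 3.29-4.71 | 4.32-5.68 | yes | 1.99 |
| 10% | 3.00-5.00 | 4.04-5.96 | yes | 1.41 |

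The two half-widths sum to 1 point at f = 0.387 (about 5,690 and 7,580 eligible patients). The interval for the difference reaches 0 at f = 0.193 (about 2,840 and 3,790). With the SAP's wave I total the two thresholds are 0.422 and 0.212. At f = 10% the difference is −0.39 to 2.39 points (p = 0.16). Overlap of two intervals is a stricter criterion than an interval for the difference, so both are shown.

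**Step 3: add clustering.** Mean cluster size m = f × total/hospitals; design effect = 1 + (m − 1) × ICC; the variance is multiplied by it.

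At f = 100%, m = 111.4, 89.5 and 75.6:

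- ICC 0.01: 3.54-4.46% and 4.58-5.42%, still separate; difference 0.38 to 1.62 points.
- ICC about 0.016: the intervals touch; the difference is still 0.29 to 1.71 points (p = 0.006).
- ICC about 0.042: the interval for the difference reaches 0.

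Both corrections together, ICC at which the interval for the I-II difference reaches 0:

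| f | ICC |
|---|---|
| 50% | 0.032 |
| 40% | 0.027 |
| 30% | 0.019 |
| 25% | 0.012 |
| 20% | 0.002 |

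At f = 10% an ICC of 0.02 moves the difference only from (−0.39, 2.39) to (−0.51, 2.51), so there the denominator is the main cause.

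**Step 4: wave II versus III.** At ICC 0.20 the 23-point difference is 19.86 to 26.14 points with f = 100%, and 19.23 to 26.77 with f = 10%.

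**Simplifications.** Equal hospital sizes and independent waves. Unequal sizes widen the intervals; hospitals that return in a later wave narrow the interval of a difference.

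**The case against.** The strongest reply is that the two parts are not equally firm. The denominator error can be shown from the documents; the size of any clustering effect cannot, since no ICC is given. At the full N, clustering alone does not bring the I-II difference to zero until the ICC is about 0.042. That stands, and the denominator is the primary point here.

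The analysis may already handle clustering. Text after protocol 9.7.1 is redacted, the SAP runs from 11.1 to 11.3, and its tables run from 1 to 3.1. This stands for the SAP, so the change there is conditional. It does not rescue 9.5, which is fully readable.

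The hospitals are a convenience sample, and protocol 9.9 already urges caution. A cluster variance does not turn such a sample into a national one, and for describing the participating hospitals alone the clustering point falls away. The denominator point holds whatever the target.

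Repeated hospitals could make the clustered thresholds pessimistic. Protocol 9.6 counts 491 hospitals, while 132 + 219 + 201 = 552; if 491 means distinct hospitals, at least 61 entries are repeats. Unequal hospital sizes act in the opposite direction, so the ICC thresholds are approximate.

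Finally, the study is descriptive, and Table 1 will report the actual n/N, so the wrong N does not carry into the results. This is true and limits the consequence. Protocol 9.5 nevertheless publishes intervals and draws a conclusion from them.

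**Conclusion.** The concern holds. The 9.5 intervals carry the wrong denominator for the proportion they describe and make no allowance for hospitals; both make the stated precision too favourable, the second when inference goes beyond the participating sites. Whether waves I and II can be told apart is open. With independent patients their intervals overlap below about 39% eligible and the interval for the difference includes zero below about 19%; clustering raises that second threshold. These figures rest on an assumed common eligible share, an assumed ICC, equal hospital sizes and independent waves. The separation of wave III is not in doubt. Confidence is high for the 9.5 statement and lower for the SAP part, because of the redactions. The correction should be made, but it changes neither the study population nor the outcomes.

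**What to change.** **Protocol 9.5 and abstract.** Recompute the intervals on the expected B and B' counts per wave over a stated ICC range, or limit the statement about distinguishing waves to II versus III.

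**SAP 11.1 and Tables 1, 3.1, 3.2.1 and 3.2.2 (the row for DTN ≤ 60 min), unless redacted text already does this.** Compute 95% CIs for proportions with hospital as the cluster, for example PROC SURVEYFREQ with CLUSTER hosp_id, and report between-wave differences with cluster-robust 95% CIs. Use one identifier per hospital across waves; the pooled ALL column needs it too.

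**Cost.** A wording change in the protocol and a procedure change in the SAP. The variable hosp_id is already in the SAP dictionary, and the B and B' counts come from existing data. Intervals will be wider, and the wave I interval for DTN ≤ 60 min will be imprecise if few patients were treated: at f = 10%, 14704 × 0.10 × 0.04 ≈ 59. Clustered intervals do not make the three convenience samples comparable, so the caution in protocol 9.9 must stay.
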